## **Objectives**

The aim of this study is to compare physiological responses in children during the administration of buffered (with sodium bicarbonate) versus non-buffered local anesthetic (LA) control by recording and comparing changes in vital signs and physical movements in pediatric patients undergoing a dental procedure under deep sedation.

## **Background**

The ability to manage pain for the pediatric patient during routine dental procedures can have a profound effect on the child's behavior during current and future appointments. Many adults with dental fears and anxiety recall experiencing negative dental experiences during childhood. However, it is difficult to determine whether successful pain management is achieved in children due to their emotional or cognitive developmental levels. Younger children are often unable to provide reliable feedback on a self-reported pain scale when asked to rate their pain perception. The body's response to stress and anxiety during administration of LA can be detected by changes in physiological responses, such as blood pressure (BP), heart rate (HR) and respiratory rate (RR). The anesthesiology team routinely responds to the child's vitals and movements, that if triggered by pain during the injection of a local anesthetic, may lead to administration of additional sedative medications during treatment. Therefore, by monitoring changes in vital signs during the administration of local anesthetic agents may be more reliable to represent the level of pain that a child receives.

Local anesthetics (LAs) are the safest and the most effective medicine to prevent and manage pain. It has been routinely used for all the dental procedures. LA exists in two forms after injections: unionized form which is lipid soluble and ionized form which is not lipid soluble. Only the unionized form can cross the nerve membrane to block nerve conduction and prevent pain. The equilibrium between the two forms is dependent on the PH of the solution. LA used in dentistry is packaged in acidic solution (PH=3.85) to prevent oxidation of the vasoconstrictor, epinephrine. For anesthesia to take effect, the body must buffer the anesthesia near physiological PH (3.85 to 7.35-7.45). Therefore, the acidity of the anesthesia may delay the onset, contribute to injection burning sensation into soft tissues. Adding bicarbonate (8.4% sodium bicarbonate; approximately 1: 9 ratio) is a simple and affordable way to decrease pain of injections. Empirical evidence including a systematic review has concluded buffered LAs with sodium bicarbonate are more effective than non-buffered LAs in adult patients. However, limited studies have evaluated the effects of buffered LAs in children during procedures in the chair or under sedation and the results are conflicting. One of the reasons could be that children are not able to report pain on a reliable quantifiable scale.

Measuring physiological responses (vital sign changes or physical movements due to pain reflex) upon LA administration could be a more reliable alternative. It has been showed that buffered or unbuffered local anesthetic may signify differences in pain perception that can be noted by measuring physiological responses in children. Pediatric Sedation Unit (PSU) at Rainbow Babies and Children's Hospitals uses propofol to deep-sedate pediatric patients that have extensive dental restorative needs. Because

propofol is a sedative agent without potent and long-lasting analgesic effect, intra-oral LA injections are necessary to control for pain caused during invasive dental procedures in PSU. In addition, children's vital signs are monitored throughout the sedation procedure. In this study, we are going to evaluate and compare the changes in vital signs and physical movements in children during the administration of buffered anesthetic versus nonbuffered LA.

	Inclusion Criteria
1.	Age range: 2-6 year old
2.	Healthy children or children with mild controlled systemic illness
3.	Treatment planned to receive restorative work on both sides of mouth (left vs right) under deep sedation, requiring local anesthetic administration

	Exclusion Criteria
1.	Children present with any illness or symptoms that can alter pain perception such as pain in head and neck area due to TMJ disorders, arthritis, autoimmune diseases.
2.	Antibiotic premedication requirement
3.	History of taking medications (NSAIDs, narcotics, sedatives, and antianxiety or antidepressant medications) that may affect anesthetic assessment.
4.	Has signs of dental pain, odontogenic abscess or facial cellulitis
5.	Allergy to local anesthetics or sulfites

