## **Study Design**

This is a prospective, single visit, randomized, double-blind split mouth study.

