## **Study Procedures**

I. All standard of care dental procedures will be followed for enrolled patients except as noted below:

1. IDS will dispense two types of local anesthetic solutionsto dental providers blindly: control solution (non-buffered LA, 2% lidocaine with epinephrine 1:100,000)) and test solution (buffered LA). Both types of solution will be administered to each subject. The types of solutions are labelled with numbers and the research team will remain blind to the type until the study is over.

2. The test solution will be made by a mixing pen called "Onset" (Onpharma Inc., Los Gatos, CA., USA), which is an FDA- approved device (see attachments). IDS will use a cartridge of 2% lidocaine with epinephrine 1:100,000 alkalinized at 9:1 ratio with a resulting pH of 7.21 using 8.4% sodium bicarbonate solution per manufacturer. This mixing pen Onset will deliver 0.18 mL of sodium bicarbonate solution into the anesthetic cartridge.

3. A dental provider will use a randomized coin flip to choose between the blindly labeled anesthetic agents to anesthetize one side of the mouth (left vs right). In addition, the sides of mouth will also be randomly selected by the toss of a coin. After the appropriate blind anesthetic solution has been selected, the same solution will be used to anesthetize each side of the mouth. In general, one cartridge of local anesthetic is sufficient to provide adequate anesthesia for 2 quadrants, however IDS will provide 2 cartridges of each solution in the event that a second cartridge of the same solution is needed. Maximum recommended dosage for local anesthetic will be calculated and followed for each patient. The provider will subsequently anesthetize the opposite side of the mouth with the opposite solution. The sequence used to administer the anesthetic will be inconsequential as the evaluation of pain will remain consistent due to the separation of nerve innervations in the posterior jaw.

4. Two researchers are required to present for each study. One researcher will be the provider who administrates LA and the other will be recording vital signs and physical movements during the injection (see point IV below).

II. In PSU, patients will be monitored per standard of care. This study does not cause potential interference with sedation monitoring.

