III. The only additional device used in this study is Onset mixing system. The Onset device is already FDA-approved for pH buffering dental local anesthetic agents with sodium bicarbonate (see attachments).

IV. Data for this study will come from the EMR, the SDM, and intra-operative data collection sheets.

1. Vital signs, which are already recorded per standard of care at baseline and every 5 minutes, will be recorded manually for significant operative events by researchers on an intra-operative data collection sheet. Significant operative events includes: topical anesthesia, injection (needle puncturing the oral mucosal tissues), delivery of both buffered and conventional local anesthesia, surgical procedures (including tooth preparation, pulpal treatment, and tooth extractions). The necessity of additional local anesthesia delivery will also be noted.

2. Modified Behavioral Pain Scale (BPS) and Pediatric Sedation State Scale (PSSS) are valid and reliable tools in the assessment of pain in the unconscious sedated patient and monitor patient's comfort level during sedation, will be recorded on intra-operative data collection sheet by study personnel during the significant operative events as listed above. We removed the ventilation compliance in BPS form since this is not applicable in our study.

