### **Data to be Collected for your study (AFTER consent and HIPAA Authorization have been obtained)**

Age, medical history, diagnosis, vital signs, behavioral pain scale.

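### The two sides of a child's mouth need not be alike in jaw or injection technique and the analysis does not adjust for this, so unlike sides add avoidable variance, though not bias, to a 20-child comparison.

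*Combined protocol and SAP*

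**What the plan says.** The Study Design section states: "This is a prospective, single visit, randomized, double-blind split mouth study". The only eligibility rule about the two sides is Inclusion Criteria item 3: "Treatment planned to receive restorative work on both sides of mouth (left vs right) under deep sedation, requiring local anesthetic administration". It sets no condition on jaw, tooth, injection technique, number of quadrants or type of procedure.

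Study Procedures, I.3, describes the allocation. First, "A dental provider will use a randomized coin flip to choose between the blindly labeled anesthetic agents to anesthetize one side of the mouth"; second, "the sides of mouth will also be randomly selected by the toss of a coin". The opposite side gets the other solution. On quantity it says: "In general, one cartridge of local anesthetic is sufficient to provide adequate anesthesia for 2 quadrants", with a second cartridge of each solution held in reserve. The one remark on comparability is that "the evaluation of pain will remain consistent due to the separation of nerve innervations in the posterior jaw". It is offered as the reason why the order of the two solutions does not matter; it is not a rule for matching sites.

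Study Procedures, IV.1, has readings taken at needle puncture, at delivery of the anesthetic and at "surgical procedures (including tooth preparation, pulpal treatment, and tooth extractions"). The Data to be Collected section lists "Age, medical history, diagnosis, vital signs, behavioral pain scale". The Data Analysis Plan compares changes in vital signs and pain scores by independent-samples t-tests, without pairing and without a term for jaw, injection type or procedure. It does not say which readings represent a side when that side has several injections. Enrolment is 20 children.

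**The concern.** A split-mouth comparison is efficient because each child serves as his or her own control. That efficiency is greatest when the two sides differ only in the solution. Here a child may qualify with the upper jaw treated on one side and the lower on the other, or with one quadrant on one side and two on the other. If responses differ by site or technique, that child's left-right difference is the solution effect plus or minus a site effect, and nothing in the planned analysis separates them.

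The stated objective is the response during administration of the anesthetic, so unlike injections bear on it directly. Unlike dental procedures bear only on the later surgical readings. What is at stake is precision: a noisier estimate from a small sample, some of which could be recovered if the site and technique of each injection were recorded and used.

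**Working it through.** The documents state no SD, effect size or power, so there is no figure of the plan's own to reproduce. The arithmetic below illustrates the mechanism on assumed inputs.

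**Inputs**
- n = 20 children (Number of Research Participants).
- Significance level 0.05 (Data Analysis Plan); two-sided is assumed.
- Solution allocated to side by coin toss (Study Procedures, I.3).
- Assumed, for heart-rate response: s, the SD of the within-child difference when sides are alike, 6 to 12 bpm; p, the share of children with unlike sides, 0.25 to 0.75; d, the effect of the site or technique difference, 4 to 12 bpm.

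**Step 1: bias.** In a child with unlike sides, the coin decides whether d is added or subtracted, each with probability 1/2, so its expected contribution is zero. In a simulation of 40,000 trials with no solution effect, with 10 or all 20 children having unlike sides and a site effect of 1.0 or 1.5 SD, a paired test rejected 5.1% to 5.2% of the time. There is no systematic bias and no inflation of type I error.

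**Step 2: variance.** The variance of the within-child difference becomes s² + p·d². The effective sample size is 20·s²/(s² + p·d²).
- Middle case (s = 8, p = 0.5, d = 8): variance 64 + 32 = 96, SD 9.8 bpm; effective n = 20 × 64/96 = 13.3.
- Mild end (s = 12, p = 0.25, d = 4): 20 × 144/(144 + 4) = 19.5.
- Severe end (s = 6, p = 0.75, d = 12): 20 × 36/(36 + 108) = 5.

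This describes the variability of the difference in means, which is the same number whether the two sets of 20 readings are then tested as paired or as independent.

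**Step 3: the same term seen as chance imbalance.** The SD of the shift in the mean difference is d·√(20p)/20. In the middle case it is 8 × √10/20 = 1.26 bpm. This is not an additional harm. The standard error rises from 8/√20 = 1.79 to 9.8/√20 = 2.19 bpm, and √(2.19² − 1.79²) = 1.26. For scale, if 10 children have unlike sides, the more reactive site falls 7:3 or worse to one solution with probability 2 × (1 + 10 + 45 + 120)/1024 = 352/1024 = 34%. A valid within-child interval already allows for this.

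**Step 4: power, on a standardized scale.** With alike sides, a paired t-test on 20 children has 80% power for a difference of 0.66 SD. With 10 of 20 children having unlike sides:

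| Site effect (SDs of the within-child difference) | Variance factor | Power at 0.66 SD | Pairs needed for 80% |
|---|---|---|---|
| 0.5 | 1.125 | 75% | 23 |
| 1.0 | 1.5 | 63% | 29 |
| 1.5 | 2.125 | 49% | 41 |

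The middle row corresponds to the middle case of Step 2 (96/64 = 1.5).

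**The case against.** The strongest reply is that randomisation already deals with this. That stands as far as bias goes. A reader might infer that solution and injection type are confounded; with both coin tosses done as described, they are not.

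The reply also says that the magnitude is all assumption. That stands too. The documents do not name the injection techniques, do not say that some provoke more response than others in deeply sedated children, and do not say how often sides will differ. One cartridge covering two quadrants, and the Background's description of extensive restorative needs, suggest that many children will have both jaws treated on both sides. The share with unlike sides could then be small. Even so, each such side yields several readings, and the plan does not say how they are combined.

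Three further inferences go beyond the documents:
- **An extraction on one side against a filling on the other.** Item 3 requires restorative work on each side, so a side with an extraction alone would not qualify. An extraction added to restorative work would affect the surgical-phase readings, not the response to the injection.
- **Injection details are not recorded.** The Data to be Collected list is a summary; it also omits the sedation scale and the need for further anesthetic, which Study Procedures, IV, says are recorded. The intra-operative sheet is not in the documents, and the medical record may hold some of these items.
- **The future trial will be mis-sized.** If that trial enrols under the same criteria and uses the same analysis, variability that includes unlike sides is the right planning input.

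What remains is that no matching or adjustment is planned, whatever the sheet records.

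**Conclusion.** The point holds as one of precision. The protocol allows the two sides to differ in jaw, technique and number of quadrants, and the planned t-tests leave that difference in the error. It does not bias the comparison, provided the coin tosses are carried out as described. The cost depends on three quantities that the documents do not give. Over the assumed ranges, the 20 children carry the information of between 19.5 and 5 children with alike sides. The lower figure needs three-quarters of children to have unlike sides and a technique effect twice the matched SD, so it is an extreme and not an expectation. If responses do not depend on site or technique, nothing is lost. This is a cheap improvement of low to moderate priority.

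**What to change.** **Data collection sheet (Study Procedures, IV).** Confirm that it records jaw, injection technique and volume for each injection, and procedure type for each surgical event, by side. Add the fields if they are absent, preferably before the first child is treated, since such details may be hard to recover later.

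**Data Analysis Plan, injection phase.** Replace the unadjusted t-test with one within-child model using all injections: child as a random effect or block, with fixed terms for solution and injection type (jaw and technique). Because solution is allocated to a side, add a term for side within child where a side contributes more than one injection, so that repeated injections are not counted as independent. With this model, no child is dropped and nobody has to choose which injections form a matched pair.

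**Data Analysis Plan, surgical phase.** Add a procedure-type term, or report these readings descriptively by procedure.

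**Cost.** A few fields on a sheet already being filled in, one or two degrees of freedom, and somewhat more analysis work than a t-test. The adjustment recovers precision only to the extent that site and technique affect the response. Eligibility and the care given do not change.

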### **Number of Research Participants**

We will enroll 20 children who were patients of the Rainbow Babies and Children's Hospital's (RBC) Tapper Dental Clinic or Dental Clinic of Rainbow Center for Women and Children.

### **Recruitment Methods**

Potential subjects will originate from the clinical practice of the study investigators in Tapper Dental Clinic at Rainbow Babies and Children's Hospital (RBC) or in Dental Clinic at Rainbow Center for Women and Children (RCWC). Research subjects are those patients who are recommended to receive dental surgery under deep sedation by the dentists and this treatment plan is accepted by their legal guardians. The legal guardian(s) of research subjects will be approached by research members right after the consultation appointment at the dental chair side. There are no planned recruitment materials aside from consent forms.

### **Setting**

Research activities will be conducted at UHCMC and outpatient facilities of the study investigators. Recruitment and consent will occur in the clinic of study investigators. Study measurement will occur at RBC in the Pediatric Sedation Unit. Data collection from the EMR will occur at UHCMC.

## **Study Design**

This is a prospective, single visit, randomized, double-blind split mouth study.

## **Study Procedures**

I. All standard of care dental procedures will be followed for enrolled patients except as noted below:

1. IDS will dispense two types of local anesthetic solutionsto dental providers blindly: control solution (non-buffered LA, 2% lidocaine with epinephrine 1:100,000)) and test solution (buffered LA). Both types of solution will be administered to each subject. The types of solutions are labelled with numbers and the research team will remain blind to the type until the study is over.

2. The test solution will be made by a mixing pen called "Onset" (Onpharma Inc., Los Gatos, CA., USA), which is an FDA- approved device (see attachments). IDS will use a cartridge of 2% lidocaine with epinephrine 1:100,000 alkalinized at 9:1 ratio with a resulting pH of 7.21 using 8.4% sodium bicarbonate solution per manufacturer. This mixing pen Onset will deliver 0.18 mL of sodium bicarbonate solution into the anesthetic cartridge.

3. A dental provider will use a randomized coin flip to choose between the blindly labeled anesthetic agents to anesthetize one side of the mouth (left vs right). In addition, the sides of mouth will also be randomly selected by the toss of a coin. After the appropriate blind anesthetic solution has been selected, the same solution will be used to anesthetize each side of the mouth. In general, one cartridge of local anesthetic is sufficient to provide adequate anesthesia for 2 quadrants, however IDS will provide 2 cartridges of each solution in the event that a second cartridge of the same solution is needed. Maximum recommended dosage for local anesthetic will be calculated and followed for each patient. The provider will subsequently anesthetize the opposite side of the mouth with the opposite solution. The sequence used to administer the anesthetic will be inconsequential as the evaluation of pain will remain consistent due to the separation of nerve innervations in the posterior jaw.

4. Two researchers are required to present for each study. One researcher will be the provider who administrates LA and the other will be recording vital signs and physical movements during the injection (see point IV below).

II. In PSU, patients will be monitored per standard of care. This study does not cause potential interference with sedation monitoring.

III. The only additional device used in this study is Onset mixing system. The Onset device is already FDA-approved for pH buffering dental local anesthetic agents with sodium bicarbonate (see attachments).

IV. Data for this study will come from the EMR, the SDM, and intra-operative data collection sheets.

1. Vital signs, which are already recorded per standard of care at baseline and every 5 minutes, will be recorded manually for significant operative events by researchers on an intra-operative data collection sheet. Significant operative events includes: topical anesthesia, injection (needle puncturing the oral mucosal tissues), delivery of both buffered and conventional local anesthesia, surgical procedures (including tooth preparation, pulpal treatment, and tooth extractions). The necessity of additional local anesthesia delivery will also be noted.

2. Modified Behavioral Pain Scale (BPS) and Pediatric Sedation State Scale (PSSS) are valid and reliable tools in the assessment of pain in the unconscious sedated patient and monitor patient's comfort level during sedation, will be recorded on intra-operative data collection sheet by study personnel during the significant operative events as listed above. We removed the ventilation compliance in BPS form since this is not applicable in our study.

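### The provider who injects also allocates, by coin toss: there is no list, no required record of the toss, and nothing to ensure that side and order balance in 20 children

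*Combined protocol and SAP*

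**What the plan says.** The Study Design section reads: "This is a prospective, single visit, randomized, double-blind split mouth study". Study Procedures I.1 adds: "Both types of solution will be administered to each subject". The sample size is stated as "We will enroll 20 children" (Number of Research Participants).

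Allocation is described only in Study Procedures I.3:

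- Solution: "A dental provider will use a randomized coin flip to choose between the blindly labeled anesthetic agents to anesthetize one side of the mouth".
- Side: "the sides of mouth will also be randomly selected by the toss of a coin".
- Second injection: "The provider will subsequently anesthetize the opposite side of the mouth with the opposite solution".
- Between these stands a sentence saying that "the same solution will be used to anesthetize each side of the mouth".

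I.4 identifies the injector: "One researcher will be the provider who administrates LA and the other will be recording vital signs and physical movements during the injection". IDS makes up the buffered cartridges, dispenses both solutions under number labels, and supplies two cartridges of each. It is given no part in choosing solution, side or order.

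I.3 also declares that the sequence does not matter, because the two sides of the posterior jaw are innervated separately. The Data Analysis Plan compares the solutions by independent t-tests, with no term for side or order. Neither the list of data to be collected nor the description of the intra-operative sheet (Study Procedures IV) mentions the toss result, the assigned label, or the side and order assigned.

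**The concern.** In a split-mouth trial, random assignment of solution to side and order is what separates the effect of the solution from differences between the sides and between the first and second injection. Here the person who will inject generates that assignment, case by case, and the plan asks for no trace of it. An unwelcome toss could be repeated unseen. The per-patient compliance check promised under the safety-monitoring section has no recorded assignment against which to compare what was given.

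The argument that sequence is harmless covers less than it needs to. Separate innervation bears on local nerve block. Heart rate, blood pressure and respiratory rate are whole-body measures. The Background section itself says that a reaction to an injection may lead the anesthesiology team to give more sedative. The second injection may therefore be observed at a different depth of sedation from the first. The analysis does not adjust for order or side, so balance by design is the only safeguard, and two simple tosses do not ensure it.

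**Working it through.** The plan gives no figure for allocation balance and declines a power analysis, so there is no stated number to reproduce. The check is how uneven two fair coins can be in 20 children, and what that could do to the comparison.

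**Inputs.** n = 20 children (Number of Research Participants). Two independent tosses with probability 0.5 each (Study Procedures I.3). One toss settles which label is used first and the other which side is first. Whether buffered goes first and whether buffered goes on the left are then two independent fair splits.

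**One factor (order or side).** P(split of r : 20−r or worse) = 2 × P(X ≤ 20−r), X ~ Binomial(20, 0.5).

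- Exactly 10:10: C(20,10)/2^20 = 184,756/1,048,576 = 17.6%.
- 13:7 or worse: 2 × 137,980/1,048,576 = 26.3%.
- 14:6 or worse: 2 × 60,460/1,048,576 = 11.5%.

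**Either factor.** 1 − (1 − p)².

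- 13:7 or worse on side or order: 1 − (1 − 0.263)² = 45.7%.
- 14:6 or worse on side or order: 1 − (1 − 0.115)² = 21.7%.
- Both exactly 10:10: 0.176² = 3.1%.

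**Four sequences (buffered first or second, by buffered left or right).**

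- Exactly 5/5/5/5: 20!/(5!)^4/4^20 = 1.1%.
- At least one sequence with 2 or fewer children: about 35% (1,000,000 simulated multinomial draws, four cells of 0.25).

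**Effect on the comparison.** Let π be the first-minus-second injection effect, in units of the SD of the within-child difference (buffered minus control) apart from order. The shift in the mean difference is π × (n buffered first − n buffered second)/20. The documents give no value for π; 0.25 to 1.0 is assumed.

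| Split | π = 0.25 | π = 0.5 | π = 1.0 |
|---|---|---|---|
| 12:8 (factor 4/20) | 0.05 SD | 0.10 SD | 0.20 SD |
| 14:6 (factor 8/20) | 0.10 SD | 0.20 SD | 0.40 SD |

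The standard error of a paired mean with 20 children is 1/√20 = 0.22 SD. Averaged over all possible tosses the shift is zero. Its variance is π²/20, so the variance of the unadjusted mean difference is multiplied by 1 + π²: 1.06, 1.25 and 2.00 for the three values of π.

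**The two sentences in I.3.** Taken literally, one has a single solution used for each side, and the next has the opposite solution on the opposite side. Only the second fits the split-mouth design and the statement in I.1 that each child receives both. The first probably means one solution throughout a given side.

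**The case against.** The strongest reply is that little can go wrong. Consent is sought after the consultation, before any injection. Every child gets both solutions, and the number labels hide which is which until the study ends. A re-toss therefore only moves an unidentified label to another side or order. That stands, and it rules out several stronger readings:

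- A reader might infer that allocation is unconcealed in the usual sense. The toss cannot influence who enters or who receives buffered anesthetic. Steering would systematically favour one solution only if the operator had guessed the code. The text leaves open whether a number keeps the same meaning for all children.
- A reader might infer that the allocation is unbalanced or biased. Fair coins balance in expectation; what is missing is assurance of balance in this one sample.
- A reader might infer that nothing can be traced. Study Procedures IV makes delivery of each anesthetic a recorded event, and the planned analysis needs the label used. The list of data to be collected is also a brief summary. The gap is narrower: no record of what was assigned.
- A reader might infer that the tosses take place in the sedation unit, or that the operator knows which side is harder. Neither is stated; the Setting section places only study measurement in that unit.
- A reader might infer from the same-solution sentence that a child could provide no comparison. The design statement and the following sentence make the intent clear; it is a drafting slip.

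Two further points stand. No analysis by the four sequences is planned, so the 35% figure describes sparse cells and has no direct consequence for a test. And the size of any order effect is assumed. Still, neither masking nor each child serving as its own control removes the chance imbalance or creates a record of the assignment.

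**Conclusion.** The point holds as a cheap improvement to a pilot, not as a flaw that undermines it. The injecting provider allocates, no list exists in advance, the plan requires no record of the assignment, and nothing ensures balance of side and order. The main cost is chance imbalance and lost precision: an 11.5% chance of 14:6 or worse on one factor and 21.7% on side or order, assuming fair and independent tosses in all 20 children. At 14:6 an order effect of 0.25 to 1.0 SD would move the estimate by 0.10 to 0.40 SD, that is, from under half to nearly twice the paired standard error. That range is an assumption; the documents neither supply an order effect nor give an argument that excludes one for systemic outcomes. The risk from an unseen re-toss is real but cannot be sized from the documents, and it depends on the label code being guessed.

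**What to change.** - Replace both tosses with a computer-generated list held by IDS. Block it over the four sequences (buffered first or second, by buffered left or right), five children each, and do not disclose the block boundaries to the clinical team.
- Have IDS dispense the cartridges already marked with order and side, still under number codes; the provider follows the marks.
- Add fields to the intra-operative sheet for the assigned and the used label, side and order of each injection, so that the per-patient compliance review can compare them.
- Reconcile the two sentences in I.3 so that both match the split-mouth design, and drop or justify the claim that sequence does not matter.

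The cost is one list, two more items on labels that IDS already produces, a few fields on the sheet and one revised paragraph. IDS must know of each case before dispensing. The blocked list gives 10:10 on order and on side only if all 20 children are analysed; the withdrawal section sets aside the data of children withdrawn for recording errors, so some imbalance could return.
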